DRUG UTILISATION AND SAFETY STUDY OF MYSIMBA/CONTRAVE IN EUROPE AND THE UNITED STATES

Protocol Number: NB-451 Version: Draft 4.0

Sponsor: Currax Pharmaceuticals LLC*

[name],

[name]

[name] [contact]

[contact]

This submission contains CONFIDENTIAL material and information and should be restricted in its distribution. Do not copy without the permission of the Sponsor.

* Orexigen Therapeutics Ireland Limited (OTIL, based in Dublin Ireland EU) is the Marketing Authorization Holder (MAH) for Mysimba[®]/Contrave[®] (naltrexone HCl/ bupropion HCl prolonged-release tablets) and is a subsidiary of Nalpropion Pharmaceuticals LLC., which is headquartered in the United States of America (USA).

PASS Information

Title	Drug Utilisation and Safety Study of Mysimba/Contrave in			
Title	Europe and the United States			
Protocol version identifier	NB-451			
Date of last version of	August 7, 2023			
protocol	11ugust 7, 2025			
EU PAS register number	EUPAS103743			
Active substance	ATC code: A08AA62			
	Prolonged-release Mysimba/Contrave is a fixed-dose			
	combination of naltrexone hydrochloride [HCl] and			
	bupropion HCl			
Medicinal product	Mysimba®/Contrave® 8 mg/90 mg prolonged-release tablets			
Product reference	EU/1/14/988/001-002			
Procedure number	EMEA/H/C/003687/MEA/003.11			
Marketing authorisation	Orexigen Therapeutics Ireland Limited / Currax			
holder(s)	Pharmaceuticals, LLC			
Joint PASS	No			
Research question and	The primary objectives of the study are:			
objectives	 To describe demographic and baseline characteristics of patients initiating use of Mysimba/Contrave. To evaluate patterns of Mysimba/Contrave initiation and use, including estimating the number and percentage of patients compliant and non-compliant with the SmPC. 			
	 The secondary objectives of this study are: To assess and compare the observed incidence AESIs in usual clinical practice among users of Mysimba/Contrave compliant and non-compliant with the SmPC. To assess the proportions of patients in the following groups who are at increased risk for AESI and to describe the characteristics of the patients with AESI: a. Any user of Mysimba/Contrave; b. Users compliant with SmPC; and c. Users out of compliance with SmPC, as described above. 			
	 5. To assess the duration of Mysimba/Contrave use. 6. To identify to the extent possible within the data sources: Initial titration scheme and proportion aligned with SmPC; 			

2. ABBREVIATIONS

AESI Adverse Events of Special Interest

BMI Body Mass Index

CI Confidence Interval

EC Ethics Committee

EMA European Medicines Agency

EU European Union

GDPR General Data Protection Regulation

GVP Good Pharmacoviglance Practice

ICMJE International Committee of Medical Journal Editors

MAH Market Authorisation Holder

MAOI Monoamine Oxidase Inhibitor

MDD Major Depressive Disorder

MedDRA Medical Dictionary for Regulatory Activities

PRAC Pharmacovigilance Risk Assessment Committee

SmPC Summary of Product Characteristics

US United States

3. DRUG DESCRIPTION

Generic Name: naltrexone hydrochloride and bupropion hydrochloride extended-release tablet

Trade Name: MYSIMBA®/Contrave®

Indications for Use:

Mysimba/Contrave is indicated as an adjunct to a reduced-calorie diet and increased physical activity for chronic weight management in adults with an initial body mass index (BMI) of:

1. 30 kg/m² or greater (obese) or

2. 27 kg/m² or greater (overweight) in the presence of at least one weight-related comorbidity (e.g., hypertension, type 2 diabetes mellitus, or dyslipidemia).

Limitations of Use:

- 1. The effect of Mysimba/Contrave on cardiovascular morbidity and mortality has not been established.
- 2. The safety and effectiveness of Mysimba/Contrave in combination with other products intended for weight loss, including prescription drugs, over-the-counter drugs, and herbal preparations, have not been established.

4. SYNOPSIS

Title:	Drug Utilisation and Safety Study of Mysimba in Europe and Contrave in the United States
Purpose:	Results from this study will add further definition and clarity to the overall safety profile of Mysimba/Contrave, to inform the MAH's view on the following: 1. to further refine the risk management and pharmacovigilance planning for this product; and 2. to determine whether the SmPC should be revised, based on the available post-marketing evidence, with the objective of optimizing the safe and effective use of the product.
Objectives and Endpoints:	The primary objectives of the study are: 1. To describe demographic and baseline characteristics of patients initiating use of Mysimba/Contrave. 2. To evaluate patterns of Mysimba/Contrave initiation and use, including estimating the number and percentage of patients compliant and non-compliant with the SmPC. The secondary objectives of this study are: 3. To assess and compare the observed incidence of AESIs in usual clinical practice among users of Mysimba/Contrave compliant and non-compliant with the SmPC. 4. To assess the proportions of patients in the following groups who are at increased risk for AESI and to describe the characteristics of the patients with AESI for all users: a. Any user of Mysimba/Contrave; b. Users compliant with SmPC; and c. Users out of compliance with SmPC, as described above. 5. To assess the duration of Mysimba/Contrave use. 6. To identify to the extent possible within the data sources: o Initial titration scheme and proportion aligned with SmPC; o Dose adjustment in special populations and proportion aligned with SmPC; o Reasons for treatment discontinuation; and o AESIs that may have led to treatment discontinuation.
Population:	Users of Mysimba/Contrave with at least 365 days of computerized records prior to first use in Denmark Finland, Norway and Sweden, and other countries (if meeting the threshold for patients and agreed upon

Power and Sample Size:	between EMA and MAH) with sufficient uptake of Mysimba/Contrave in the respective national health systems. Additionally, U.S. data will be included. The study will include data from approximately 3,000			
rower and Sample Size.	patients per database. Only databases with at least 750 patients will be included in the analysis.			
Anticipated Study Duration:	3 years (based on current uptake in Denmark, Finland, Norway, and Sweden); study follow-up of 18 months			
Treatment:	Mysimba/Contrave			
Inclusion/Exclusion Criteria:	Patients will be included in the study if they meet the following inclusion criteria: 1. At least one prescription of Mysimba/Contrave in his/her medical records any time during the study period; 2. At least 365 days of computerized records prior to first prescription/dispensing of Mysimba/Contrave (index date); and 3. Patient is active (i.e., alive and registered/accruing data) at index date.			
	All patients meeting inclusion criteria will be included in the study; no exclusion criteria will be applied.			
Safety Assessments:	The incidence rate of adverse events of special interest (AESI) per person-years of exposure after initiation of Mysimba/Contrave will be assessed. Additionally, overall and for each type of AESI, the crude incidence of new AESIs will be reported as the incidence proportion, which will be reported over the empirical follow-up time and with 95% CI.			
Data Analysis:	For demographic and baseline variables, descriptive statistics will be used to describe categorical and continuous variables. Descriptive analyses will be performed for all users of Mysimba/Contrave, and by use categories: (1) use inconsistent with the approved indication, and (2) use incompatible with the stated contraindications. The incidence rate (and 95% CI) of new onset comorbidities and concomitant medication after initiation of Mysimba/Contrave will be assessed. Incidence rates will be determined both for the person-years of time exposed to Mysimba/Contrave (i.e., while patient taking medication) after the index date as well as for all person time through 548 days (18 months) after the index Mysimba/Contrave prescription.			

The incidence rate (and 95% CI) of pregnancy and recorded breastfeeding after the Mysimba/Contrave index date will be assessed among females initiating Mysimba/Contrave.
The mean, standard deviation, median, mode, and interquartile range of Mysimba/Contrave medication duration will be assessed overall and by use categories. Among patients with available information, the proportion of patients with titration and dosing changes in alignment with the SmPC will be calculated.

5. AMENDMENTS AND UPDATES

The NB-451 protocol (V4.0) has been revised to include updated milestones, inclusion of the US data source, Arcadia, and changes to feasibility assessments, now that the NB-451 study is underway.

6. MILESTONES

Milestone	Nordic Registries Study	U.S. Study	
	Anticipated Dates	Anticipated Dates	
Study protocol resubmitted to EMA	November 21, 2022	November 21, 2022	
Protocol approved by EMA	December 15, 2022*	December 15, 2022*	
Registration in EU PAS Register	January 15, 2023	January 15, 2023	
Apply for registry data for secondary	September 15, 2023 (post	N/A	
use	EC approval)		
Data receipt and start date for data	December 29, 2023	February 15, 2023	
analysis			
Interim report of study results #1**	April 15, 2024	N/A	
Interim report of study results #2***	April 15, 2025	N/A	
Final report of study results****	December 31, 2025**	August 4, 2023**	

^{*} Subsequent dates are dependent on timing of protocol approval by EMA

^{**} Based on counts of patients prescribed/dispensed Mysimba/Contrave through the end of 2021 and assuming both 80% are captured in the databases and 80% of identified patients are new users with at least 365 days continuous eligibility in data source before first Mysimba/Contrave prescription/dispensing, then there should be >3,000 eligible patients in data sources from US, Norway, Finland and possibly Sweden in this

analysis; it is uncertain at this time whether there will be at least 750 patients in Denmark during the conduct of the NB-451 study. Data for this interim study report will be the data available by December 29, 2023; it is likely that data will only be available through 2021 at this time.

*** A second interim report will only be included if Denmark identifies 750-3,000 eligible patients who would be available before December 31, 2024.

**** Final report date dependent on accumulation of data from the four Nordic country databases. Based on counts to date and projections of new users, there should be >3,000 eligible patients in the Norway and Finland data sources at the end of 2023. The 2023 data from Norway and Finland are expected to be available in late 2024. If final data are available in late 2024, the December 2025 final report will include the new final results from Norway, Finland, and Sweden, with updated interim or final analyses in Denmark, if appropriate.. Additionally, the final report will provide synthesis across all four Nordic data sources.

7. RATIONALE AND BACKGROUND

According to the World Health Organisation, weight-related health issues are some of the most significant global public health challenges. Worldwide obesity has nearly tripled since 1975. Obesity (body mass index [BMI] ≥30 kg/m2) and being overweight (BMI ≥27 kg/m2 to <30 kg/m2) are linked to psychosocial conditions and are major risk factors for chronic diseases, including cardiovascular disease, orthopaedic/degenerative joint disease, and diabetes. Globally there are more people who are obese than underweight and this occurs in every region except parts of sub-Saharan Africa and Asia. The World Health Organisation estimates that the prevalence of obesity and overweight, among adult men and women in Europe, is over 20% and over 50%, respectively. The major health risks and complications associated with obesity negatively affect quality of life and reduce average life expectancy. In addition to burdening the health care system, the treatment of overweight and obesity is a public health imperative. Long-term lifestyle changes are essential to mitigate obesity-related morbidity and mortality; however, for overweight and obese individual's lifestyle changes alone are insufficient, and pharmacotherapy should be considered and added.

Mysimba/Contrave, a fixed-dose combination of naltrexone (an opioid receptor antagonist) and bupropion (a selective neuronal re-uptake inhibitor of noradrenaline and dopamine), was approved in Europe for the treatment of adults with a BMI of \geq 30 kg/m2 (obese) or \geq 27 kg/m2 to <30 kg/m2 (overweight) in the presence of one or more weight-related co-morbidities (e.g., type 2 diabetes, dyslipidaemia, or controlled hypertension).

The European Medicines Agency (EMA) requested that Orexigen Therapeutics Ireland Limited (Orexigen) provide additional information on the utilisation of Mysimba in Europe and further

characterize the safety profile of Mysimba. As a supplement to the Mysimba Risk Management Plan (RMP), Orexigen has designed this database study to address that request. This study will describe the utilization and safety of Mysimba/Contrave in a real-world setting using electronic health records (EHR) and administrative health claims in several European countries and the U.S. Available characteristics of patients initiating Mysimba/Contrave will be described, with particular focus on patients receiving Mysimba/Contrave in a manner noncompliant with the Summary of Product Characteristics (SmPC) at initiation, such as use inconsistent with labelled indication or use in patients with a contraindication to the medication. Use inconsistent with labelled or otherwise authorized indication includes, but is not limited to: age <18 years and use for a reason other than management of weight in a patient who has obesity or is overweight. Contraindications include, but are not limited to, the following: current diagnosis of uncontrolled hypertension, seizure disorder, or end-stage renal failure; history of seizures, bipolar disorder, anorexia nervosa or bulimia; current dependence on chronic opioids or opiate agonists (e.g., methadone); current state of acute opiate withdrawal; or any concomitant treatment containing bupropion, naltrexone, or a monoamine oxidase inhibitor (MAOI). This study also plans to evaluate the incidence of adverse events of special interest (AESI) in real-world settings. The incidence of seizures, suicidality (i.e., suicidal ideation, attempted

Mysimba/Contrave, to inform the MAH's view on the following:To further refine the risk management and pharmacovigilance planning for this product;

suicide or completed suicide), neuropsychiatric events (i.e., mania or depression), hepatotoxicity,

or severe hypersensitivity reactions following initiation of treatment with Mysimba/Contrave

will be investigated. Additionally, the incidence of AESIs will be evaluated in subgroups of

Results from this study will add further definition and clarity to the overall safety profile of

patients, including those who do not adhere to the conditions of use set out in the SmPC.

2. To determine whether the SmPC should be revised, based on the available post-marketing evidence, with the objective of optimizing the safe and effective use of the product.

8. RESEARCH QUESTIONS AND OBJECTIVES

The aim of the study is to assess the long-term (548 days) real-world utilization patterns of Mysimba/Contrave use among patients who are prescribed Mysimba/Contrave. There are no a priori hypotheses for this study.

The primary objectives of the study are:

- To describe demographic and baseline characteristics of patients initiating use of Mysimba/Contrave; and
- 2. To evaluate patterns of Mysimba/Contrave initiation and use, including number of prescriptions, number of treatment episodes and duration between prescriptions, as well as estimating the number and percentage of patients compliant and non-compliant with the SmPC.

Analysis of compliance to the labelled indication and contraindications will be adapted to the specific SmPC for the country relevant to the data source (s). Examples of non-compliance include, but are not limited to:

Use inconsistent with labelled indication:

- 1. Age <18 years
- 2. Use other than management of weight
- 3. Management of weight in a patient who does not have obesity or is not overweight and has a weight-related comorbidity
- 4. A prescribed maintenance dose other than the Mysimba/Contrave 32mg/360mg
- 5. Continued use past 16 weeks without \geq 5% weight loss

Use in patients with contraindications:

- 6. A current diagnosis of uncontrolled hypertension, seizure disorder (or history of seizures), or end-stage renal failure
- 7. A history of bipolar disorder, anorexia nervosa or bulimia
- 8. A current dependence on chronic opioids or opiate agonists (e.g., methadone)
- 9. A current state of acute opiate withdrawal
- 10. Any concomitant treatment containing bupropion, naltrexone, or a MAOI
- 11. Patients with a known central nervous system tumour

Proprietary and Confidential:

- 12. Patients undergoing acute alcohol or benzodiazepine withdrawal
- 13. Patients with severe hepatic impairment (dependent on local SmPC)

The secondary objectives of this study are:

- 1. To assess and compare the observed incidence of AESIs in usual clinical practice among users of Mysimba/Contrave compliant and non-compliant with the SmPC. AESIs include new onset of the following:
 - 1. Seizures
 - 2. Suicidality (i.e., suicidal ideation, attempted suicide or completed suicide)
 - 3. Neuropsychiatric events (i.e., mania or depression)
 - 4. Hepatotoxicity
 - 5. Severe hypersensitivity reaction
 - 6. Serotonin syndrome
 - 7. Major adverse cardiovascular events (i.e., cardiovascular-related death, non-fatal myocardial infarction, or non-fatal stroke)

Deaths will also be reported in patients in which vital status is known.

- 2. To assess the proportions of patients in the following groups who are at increased risk for AESI and to describe the characteristics of the patients with AESI in these groups:
 - 1. Any user of Mysimba/Contrave
 - 2. Users compliant with SmPC
 - 3. Users out of compliance with SmPC, as described above
- 3. To assess the duration of Mysimba/Contrave use
- 4. To identify to the extent possible within the data sources:
 - 1. Initial titration scheme and proportion aligned with SmPC
 - 2. Dose adjustment in special populations and proportion aligned with SmPC
 - 3. Reasons for treatment discontinuation (not typically available in these databases)
 - 4. AESIs leading to treatment discontinuation (not typically available in these databases)

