- 6. Serotonin syndrome
- 7. Major adverse cardiovascular events (i.e., cardiovascular-related death, non-fatal myocardial infarction, or non-fatal stroke)

Deaths will also be described by treatment group, for those with vital status available.

- 7. Treatment discontinuation (assessed using ATC [outpatient, Nordic data] or NDC [US data])
- 8. Reason(s) for treatment discontinuation (obtained via ICD-10 codes in the 90 days prior to discontinuation)

All variables will be identified from the data sources via a pre-specified list of definitions (i.e., code lists; see Appendix 2). Occurrence of AESI based on diagnostic codes will be summarized for all patients, and for a subgroup of patients who do not adhere to conditions of the EU SmPC for the Scandinavian countries (adapted to local SmPC as needed) or to the FDA SmPC for the US. Such criteria include: not meeting appropriate criteria for the indication [obese (BMI \geq 30 kg/m²), or being overweight (BMI \geq 27 kg/m² to < 30 kg/m²) and having at least one weight-related co-morbidity (e.g., type 2 diabetes, controlled hypertension, or dyslipidemia) based on diagnostic codes. If BMI is not available, diagnostic and procedure codes for obesity and weight loss will be applied, recognizing that it will likely produce a more obese population than would be identified by BMI. Subgroup analyses will also be conducted to assess continuous treatment in patients with either renal or hepatic impairment.

Initiation of specific medications that could result with the occurrence of an event corresponding to an AESI (e.g., newly initiating anti-epileptic/seizure medication, newly initiating medications indicated for mania or depression) will also be tabulated. For hepatotoxicity, liver function tests can be used (when available) in addition to diagnostic codes.

For reason(s) patients who discontinue treatment (i.e., do not refill their prescription), events (potential AESIs and contraindications) and clinical status (magnitude of weight loss or gain)

Proprietary and Confidential:

occurring within the 90-day window prior to discontinuation will be summarized. It should be noted that weight may not be available in the Scandinavian registries.

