9.3.3. Covariates

When available, the following variables needed to conduct analysis for the primary and secondary research objectives will be collected. Variable availability from each country will be summarized in the SAP and is included in Appendix 3 in draft form.

Demographics and Baseline variables (Within 365 days before index date unless otherwise stated below; as depicted in Figure 1):

- 9. Patient demographics (age and sex on index date) (obtained directly from data source)
- 10. BMI, height, weight (most recent value on or before the index date) (obtained directly from data sources; BMI may be calculated if height and weight available)
- 11. Relevant comorbidities (obtained via ICD-10 codes), including:
 - 1. Weight-related comorbidities (i.e, type 2 diabetes, dyslipidaemia, hypertension)
 - 2. Neuropsychiatric conditions (mania, bipolar disorder, major depressive disorder [MDD], anorexia nervosa, bulimia)
 - 3. Uncontrolled hypertension, if possible
 - 4. Moderate or severe renal impairment
 - 5. End-stage renal disease
 - 6. Seizure disorder
 - 7. Hepatic impairment (defined by Child-Pugh score category, if available)
 - 8. Central nervous system tumour

- 12. History of, or current substance abuse/dependencies including acute opiate withdrawal (obtained via ICD-10 codes)
- 13. History of uncontrolled hypertension, seizures, bipolar disorder, MDD, anorexia nervosa, or bulimia (obtained via ICD-10 codes)
- 14. Prior medication use, including: naltrexone, bupropion, CYP2B6 inhibitors, CYP2B6 inducers, CYP2B6 substrates, CYP2D6 substrates, Monoamine oxidase inhibitors, Opioids, Opium alkaloids and derivatives and drugs that lower seizure threshold (obtained via ATC [Nordic data] or NDC [US data]) see Appendix 2 and 2A
- 15. Pregnancy status and breastfeeding status (obtained via ICD-10 codes)

All variables will be identified from the data sources outlined below using a pre-specified list of definitions per database (Appendix 3), to be defined in the SAP as final.

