The proportion of users non-adherent to each component of the indication/contraindications will also be determined. Small numbers will be presented as "<x" where "x" represents the defined threshold for the smallest number of patients that is allowed to be presented from the data source. Since information on the titration scheme is expected to be sparse (and, not present in the Nordic data), a sensitivity analysis will also be conducted where the first dispensing (112 tablets) is allowed to cover the full time of titration (i.e., 7 tablets in first week (n=7 days), 14 tablets in second week, 21 tablets in third week, and the remaining 70 tablets over 17.5 days (4 tablets per day) for a total of 38.5 days). The possible gap will be 19 days (half of the days' supply) before the second dispensing. Duration of Mysimba/Contrave use and adherence will be recalculated based on this adjustment. Adherence to the titration scheme will be confirmed for a patient if the second dispensing occurs within 40 days +/- 7 days from the first dispensing. Additionally, another sensitivity analysis will be implemented in which patients with evidence of renal or liver impairment are allowed up to 56 days for consumption of *each* dispensing to account for

continued use and adherence within these patients who are unlikely to reach the full recommended dosage due to renal or hepatic dosage adjustments.

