Name of the main author of the protocol.				
Name of the main author of the protocol:				
Date: dd/Month/year				
Signature:				

15. Appendix 2. Code lists

Mysimba ATC: A08AA62 Contrave NDC: search terms – Contrave, naltrexone, bupropion Naltrexone ATC: N07BB04, A06AH01, N02AA56	
Contrave NDC: search terms – Contrave, naltrexone, bupropion	
Naltrexone ATC: N07BB04, A06AH01, N02AA56	
NDC: search terms – naltrexone	
Bupropion ATC: N06AX12	
NDC: search terms – bupropion	
Concomitant Medications	
CYP2B6 inhibitors See Appendix 2A	
CYP2B6 inducers See Appendix 2A	
CYP2B6 substrates See Appendix 2A	
CYP2D6 substrates See Appendix 2A	
Drugs that lower Propoxyphene, remifentanil, sufentanil, tapentadol, tramadol,	
seizure threshold baclofen, buspirone, dalfampridine, lithium, mefenamic acid,	
amphetamine, benzphetamine hydrocholoride, dextroamphetan	mine,
hydroxyamphetamine hydrobromide, lisdexamfetamine dimes	
methamphetamine hydrochloride, cocaine, phenylpropanolam	
dexamphetamine, methylphenidate	
Opioid or opiate ATC: N02A;	
agonist	
Opium alkaloids & ATC: R05DA, N02AA	
derivatives	
MAOI ATC: N04BD, N06AF, N06AG	
Seizures ICD-10: G40	
Increase in blood ICD-10: R00.0, R03.0	
pressure or heart rate	
Hypersensitivity, ICD-10: T78, L51	
including Stevens-	
Johnson	
Serotonin syndrome ICD-10: T43.225A	
Suicidality ICD-10: R45.851, T14.91	
Diabetes ICD-10: E10-E11	
Dyslipidaemia ICD-10: E78	
Neuropsychiatric	
conditions:	
Mania ICD-10: F30	
Bipolar disorder ICD-10: F31	

N4 : 1 :	ICD 10 F22
Major depressive	ICD-10: F33
disorder	ICD 10 F50 0
Anorexia nervosa	ICD-10: F50.0
Bulimia	ICD-10: F50.2
Hypertension	ICD-10: I10-I16
TT . 11 1	
Uncontrolled	ICD-10: I10-I16 (with Systolic ≥140 mmHg or diastolic ≥90 mmHg)
hypertension	10D 10 N10 0 N10 5
Moderate or severe	ICD-10: N18.3-N18.5
renal impairment	
End stage renal	ICD-10: N18.6
disease	
Hepatic impairment	ICD-10: K70, K72-K75
Central nervous	ICD-10: C72
system tumour	
Substance	ICD-10: F10-F19
abuse/dependency	
	ATC: N06AA11
Protriptyline*	NDC: search terms – protriptyline
Dannanidal (Anarril)*	ATC: N05AD07
Benperidol (Anquil)*	No NDC
Flupentixol	ATC N05AF01
(Depixol)*	No NDC
Fluphenazine	ATC: N05AF02
(Modecate,	NDC: search terms – fluphenazine
Prolixin)*	•
Levomepromazine	ATC: N05AA02
(Nozinan)*	No NDC
Loxapine	ATC: N05AH01
(Loxitane)*	NDC: search terms – loxapine
	ATC: N05AE02
Molindone (Moban)*	NDC: search terms – molindone
	ATC: N05AC01
Periciazine*	No NDC
Sulpiride (Dolmatil,	ATC: N05AL01
Sulpor)*	No NDC

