Appendix 3. Variable Availability by Country (final list to be confirmed in SAP)

LEGEND: "--" indicates that the information is not available

Partial = may be available for some patients

Limited = anticipated to be underreported

Yes = likely to be available if true for patient

Unlikely = available for some patients; may not be accurate

Calculated = assumptions can be used to derive a variable for this information

Variable	US	Denmark	Norway	Sweden	Finland
Mysimba prescription	Yes				
Date of Mysimba	Yes				
prescription					
Mysimba dispensing	Partial	Yes	Yes	Yes	Yes
Date of Mysimba	Partial	Yes	Yes	Yes	Yes
dispensing					
Mysimba dosage for each	Partial				
dispensing					
Initial titration scheme	Maybe				
Dosing of Mysimba during	Maybe				
titration					
Dose adjustment of	Partial				
Mysimba (e.g., for special					
population)					
Maintenance dose of	Maybe				
Mysimba					
Mysimba days' supply	Calculated	Calculated	Calculated	Calculated	Calculated
Date of	Partial	Yes	Yes	Yes	Yes
eligibility/enrolment					
available to identify					
continued					
engagement/recording of					
clinic visits					
Age	Yes	Yes	Yes	Yes	Yes
Sex	Yes	Yes	Yes	Yes	Yes
BMI	Partial				
Height	Partial				
Weight	Partial				
Diabetes	Yes	Yes	Yes	Yes	Yes
Dyslipidaemia	Yes	Yes	Yes	Yes	Yes

Proprietary and Confidential:

This document cannot be used, distributed, or reproduced in any way without the prior written consent of Currax Pharmaceuticals LLC.

Anorexia nervosa	Yes	Yes	Yes	Yes	Yes
Bulimia	Yes	Yes	Yes	Yes	Yes
Hypertension	Yes	Yes	Yes	Yes	Yes
Uncontrolled hypertension	Yes	Yes	Yes	Yes	Yes
Moderate or severe renal	Yes	Yes	Yes	Yes	Yes
impairment	1 68	1 68	1 68	1 68	1 68
End-stage renal disease	Yes	Yes	Yes	Yes	Yes
Seizure	Yes	Yes	Yes	Yes	Yes
Seizure disorder	Maybe	Unlikely	Unlikely	Unlikely	Unlikely
Hepatic impairment via	Maybe				
Child-Pugh score	Mayoc				
Hepatic impairment via diagnosis	Yes	Yes	Yes	Yes	Yes
Central nervous system	Yes	Yes	Yes	Yes	Yes
tumour					
Substance use/abuse	Limited	Limited	Limited	Limited	Limited
Acute opiate withdrawal	Limited				
Acute alcohol or	Limited				
benzodiazepine withdrawal					
Suicidality	Limited	Limited	Limited	Limited	Limited
Mania	Limited	Limited	Limited	Limited	Limited
Bipolar disorder	Limited	Limited	Limited	Limited	Limited
Major depressive disorder	Yes	Yes	Yes	Yes	Yes
Hepatotoxicity	Yes	Yes	Yes	Yes	Yes
Severe hypersensitivity reaction	Limited	Limited	Limited	Limited	Limited

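### Appendix 2 identifies two listed contraindications with codes that are too narrow: CNS tumour by C72 alone in all sources, and end-stage renal disease by N18.6 alone, a code the Nordic registers may not use.

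*Protocol*

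**What the plan says.** Section 8 lists, among uses in patients with contraindications, "A current diagnosis of uncontrolled hypertension, seizure disorder (or history of seizures), or end-stage renal failure" and "Patients with a known central nervous system tumour". Section 9.7.2 repeats both. The tumour criterion is not limited by site or behaviour.

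Under primary objective 2 the number and percentage of compliant and non-compliant users are estimated, and section 9.7.2 adds: "The proportion of users non-adherent to each component of the indication/contraindications will also be determined".

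On how conditions are found, section 9.3.2 says: "All variables will be identified from the data sources via a pre-specified list of definitions (i.e., code lists; see Appendix 2". The relevant Appendix 2 rows are:

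- End stage renal disease: N18.6 only.
- Moderate or severe renal impairment: "ICD-10: N18.3-N18.5". This condition is not among the listed contraindications.
- Central nervous system tumour: C72 only.

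Appendix 3 marks both end-stage renal disease and CNS tumour Yes for the US and all four Nordic countries, with the legend "Yes = likely to be available if true for patient". Section 9.3.3 says variables will be identified "using a pre-specified list of definitions per database (Appendix 3), to be defined in the SAP as final".

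**The concern.** The protocol names two broad clinical conditions and then fixes a single code for each. If the code covers only part of the condition, or is not in use in a register, the reported proportion reflects the code list and not prescribing. A zero or near-zero count would carry little or no information about use in these patients, yet could be read as adherence to the label. That matters because the synopsis and section 7 say the results are to inform risk management and a possible SmPC revision.

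Appendix 2 shows signs of one list serving two coding systems. Medications are separated into ATC and NDC entries, but diagnoses appear under one undivided ICD-10 label. Among them is the serotonin syndrome row, "ICD-10: T43.225A", a seven-character code in the style of the US clinical modification. Nothing in the list gives a Nordic equivalent.

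**Working it through.** **Premises from outside the protocol.** The documents do not say what the codes cover. Two premises come from the structure of the classification the protocol adopts:

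- C72 covers the spinal cord, cranial nerves and other parts of the central nervous system. Brain is C71, meninges C70, benign or uncertain CNS tumours D32-D33 and D42-D43, and brain metastases C79.3.
- N18.6 exists in the US clinical modification. WHO-based ICD-10 places end-stage disease in N18.5.

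A third premise is a plain assumption: the Nordic registers use WHO-based ICD-10.

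**Criterion against code.**

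| Criterion (section 8) | Appendix 2 code | US source | Nordic sources |
|---|---|---|---|
| Known CNS tumour, any site | C72 | Misses brain, meninges, benign or uncertain tumours, metastases | Same loss |
| End-stage renal failure | N18.6 | Usable | No patient flagged, if registers are WHO-based; patients fall in the N18.3-N18.5 row |

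The CNS tumour row does not depend on the Nordic assumption. The renal row does: a register that uses N18.6 has no such loss.

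**The protocol's own precision figure.** Section 9.5 says that no events in 3,000 patients bounds the chance of an outcome at 3/3,000 = 0.1% with 95% confidence. The exact one-sided bound is 1 − 0.05^(1/3000) = 0.0998%, so the figure reproduces. It presumes that a case, if present, would be seen. Section 9.5 states it for outcomes, but a reader could apply it to a contraindication count of zero. If the code is never used, that zero says nothing about the true proportion.

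**Size.** Let n be the number of users, p the true prevalence and s the sensitivity of the code. Then

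- found = n × p × s
- missed = n × p × (1 − s)
- largest shift in the overall compliant percentage = 100 × p × (1 − s) points, reached only if no missed patient meets another non-compliance criterion.

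The documents give neither p nor s, so both are assumed ranges. With n = 3,000 (section 9.5):

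| p | True cases | Found, s = 0 | Found, s = 0.1 | Found, s = 0.3 | Missed, s = 0 to 0.3 | Largest shift (points) |
|---|---|---|---|---|---|---|
| 0.05% | 1.5 | 0 | 0.15 | 0.45 | 1.5 to 1.05 | 0.05 |
| 0.1% | 3 | 0 | 0.3 | 0.9 | 3 to 2.1 | 0.1 |
| 0.2% | 6 | 0 | 0.6 | 1.8 | 6 to 4.2 | 0.2 |
| 0.5% | 15 | 0 | 1.5 | 4.5 | 15 to 10.5 | 0.5 |

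The column s = 0 is the Nordic renal case under the assumption. The columns s = 0.1 and 0.3 illustrate C72.

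Section 9.4.2 expects more than 20,000 US users. For CNS tumour there, 20,000 × 0.05% = 10 and 20,000 × 0.5% = 100 true cases. Missed cases would run from 10 × 0.7 = 7 to 100 × 0.9 = 90.

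**The case against.** **The SAP can still correct this.** Section 9.3.3 leaves per-database definitions to be made final there, and section 9.4.1 says the SAP must take account of the fields available through Nordic licensing. This is fair, and it bears most on N18.6, since country adaptation of codes is ordinary SAP work. It does not remove the point. Appendix 2 states specific codes that do not match the protocol's own criteria, and the C72 row is too narrow in every source. Appendix 3, which section 9.3.3 cites, lists availability and not codes.

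**The codes are not useless.** A reader might infer that neither code can find its patients. That goes too far: N18.6 works in the US source, and C72 finds some CNS tumours. Nor should all four Nordic registers be counted as certain, because section 9.4.1.1 does not expect Denmark to exceed 750 eligible users.

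**Missed patients are not all compliant.** A reader might also infer that contraindicated users enter the compliant group and raise its seizure incidence. A missed patient counts as compliant only if no other criterion applies. Seizure disorder or a history of seizures is itself a listed contraindication, with seizures coded G40, so brain-tumour patients with recorded baseline seizures are already non-compliant. The remaining effect on AESI rates cannot be quantified from the documents.

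**No multiple of understatement can be given.** Any such factor is only the reciprocal of an assumed share of CNS tumours coded C72.

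**The 56-day allowance is not affected.** Section 9.7.2 gives it as a sensitivity analysis for any evidence of renal or liver impairment. It is not tied to the N18.3-N18.5 row, and end-stage patients have renal impairment in any case.

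**Masking may hide the result.** Section 9.7.2 reports small numbers as below a threshold it does not state, so cells of this size may be masked under either code list. End-stage renal failure also shares one list item with uncontrolled hypertension and seizures. A renal zero is visible only if the conditions are tabulated separately, and otherwise disappears into the combined count. Both points limit how visible the error is. Neither makes the count right.

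**Conclusion.** The point holds as a code-list error with limited reach. C72 alone is too narrow for a known CNS tumour in all five databases; this rests only on the structure of ICD-10. N18.6 alone gives a structural zero for end-stage renal failure in the Nordic sources if those registers use WHO-based ICD-10, which should be confirmed register by register. In that case the Yes in Appendix 3 is misleading for the variable as coded.

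The damage is mainly to two component proportions under primary objective 2, which would be uninformative or too low. On the assumed prevalences, the effect on the overall compliant percentage is at most 0.05 to 0.5 points per condition, and it is probably small for AESI rates. The rows should be corrected because the stated rule gives wrong answers for these components and the change is cheap.

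**What to change.** In Appendix 2:

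1. Define CNS tumour as C70-C72, C79.3, D32-D33 and D42-D43 in all sources.
2. Define end-stage renal disease by coding system: N18.6 for the US; N18.5 plus dialysis codes (for example Z49 and Z99.2) for the Nordic registers, after confirming which ICD-10 version each register uses.
3. Limit the Nordic row for moderate or severe renal impairment to N18.3-N18.4, so that the two renal rows do not overlap.

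**Cost.** Three code rows change. Section 5 says the study is underway, and section 6 plans US data receipt for February 15, 2023 and the US final report for August 4, 2023. The CNS tumour change therefore probably means re-running the US analysis, or stating the limitation in its report; the same applies to any Nordic interim already completed. Nordic N18.5 will also include some stage 5 patients not on dialysis, so that count may run slightly high. Reporting the dialysis-coded subset alongside shows by how much.
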